5.11. Anti-drug Antibody Analysis

The results of anti-drug and neutralizing antibody testing for ACE-536 and human ActRIIB protein versus time will be presented. Exploratory analysis will be performed on the potential effect of anti-drug antibodies on ACE-536 PK and drug exposure if anti-drug antibody tests are deemed positive.

5.12. Interim Analysis

There are no planned interim analyses. However, safety and erythroid response data will be reviewed periodically throughout the study.

5.13. Protocol Violations or Deviations

Protocol violations and deviations will be reviewed and may result in a patient and/or patient visit data being excluded from the statistical summaries. All decisions regarding exclusion of any patient data will be made and recorded during the final data review.

5.13.1. Violation Criteria

Patients who meet any of the following criteria will be listed:

- Non-compliance with inclusion criteria
- Non-compliance with exclusion criteria
- Unauthorized concomitant therapy
- Less than 8 weeks historical hemoglobin data
- Dose not modified according to Dose Modification Criteria
- Study assessment outside of visit window

5.13.2. Protocol Deviations

Deviations from the protocol, as defined in the protocol, will be documented on an ongoing basis by the study monitors and project manager throughout the study period.

At the time of database lock and while the protocol violations are being reviewed, the project manager will forward all relevant documentation highlighting protocol deviations to the study statistician. These deviations will be included in the protocol violation document for agreement and will be listed with the protocol violations in the CSR.

5.14. Handling of Missing Data and Visit Window

5.14.1. Missing Data

As a general principle, no imputation of missing data for other variables will be done. Exceptions are the start and stop dates of AEs and concomitant medication. The imputed dates will be used to allocate the medication as prior or concomitant medications and to determine whether an AE is/is not treatment emergent. Listings of the AEs and concomitant medications will present the actual partial dates; imputed dates will not be shown.

5.14.2. Missing Dates for Adverse Event

Imputing partial AE start dates:

- a. If the year is unknown, the date will not be imputed and will be assigned a missing value.
- b. If the month is unknown, then:
 - If the year matches the first dose date, then impute the month and day of the first dose date.
 - Otherwise, assign January.
- c. If the day is unknown, then:
 - If the month and year match the first dose date, then impute the day of the first dose date.
 - Otherwise, assign '01'.

Imputing partial AE stop dates:

- a. If the year is unknown, the date will not be imputed and will be assigned a missing value.
- b. If the month is unknown, then assign December.
- c. If the day is unknown, then assign the last day of the month.

5.14.3. Missing Dates for Concomitant Medication

If start date is missing or partial:

- if month is missing, use January
- if day is missing, use the first day of the month under consideration
- if year is missing, use year of the informed consent date
- if entire date is missing, use informed consent date

If stop date is missing or partial:

- if month is missing, use December
- if day is missing, use the last day of the month under consideration
- if year or the entire date is missing, set to 31 December 2099

If the imputed start date is after the stop date, then the imputed start date will be one day prior to the stop date.

5.14.4. Visit Windows

The following naming conventions for visit will be presented in the tables, listings and figures. The analysis window will be used for all safety assessments. For each patient, if more than one observation exists within the analysis window, an average value will be included in the analysis.

Visit	Abbreviated Visit	Visit window
Screening (Day -28)	Screen	28 Days prior to C1D1
Cycle 1 Day 1	C1 D1	Day 1
Cycle 1 Day 8	C1 D8	Day 8 ± 3 Day
Cycle 1 Day 11 ^a	C1 D11	Day 11 ± 3 Day
Cycle 1 Day 15	C1 D15	Day 15 ± 3 Day
Cycle 2 Day 1	C2 D1	Day 22 ± 3 Day
Cycle 2 Day 8	C2 D8	Day 29 ± 3 Day
Cycle 2 Day 15	C2 D15	Day 36 ± 3 Day
Cycle 3 Day 1	C3 D1	Day 43 ± 3 Day
Cycle 3 Day 8	C3 D8	Day 50 ± 3 Day
Cycle 3 Day 15	C3 D15	Day 57 ± 3 Day
Cycle 4 Day 1	C4 D1	Day 64 ± 3 Day
Cycle 4 Day 8	C4 D8	Day 71 ± 3 Day
Cycle 4 Day 15	C4 D15	Day 78 ± 3 Day
Cycle 5 Day 1	C5 D1	Day 85 ± 3 Day
Cycle 5 Day 8	C5 D8	Day 92 ± 3 Day
Cycle 5 Day 15	C5 D15	Day 99 ± 3 Day
End of Treatment	EOT	Day 113 ± 7 Day
Post-Treatment Follow Up	PTFU	Day 141 ± 7 Day
End of Study	EOS	Day 169 ± 7 Day

^a For PK data only.

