5. STATISTICAL METHODOLOGY

5.1. Definitions

Low Transfusion Burden (LTB)

LTB patients are defined as those who received < 4 units of RBCs within 8 weeks prior to Cycle 1 Day 1.

High Transfusion Burden (HTB)

HTB patients are defined as those who required ≥ 4 units of RBCs within 8 weeks prior to Cycle 1 Day 1.

Baseline Hemoglobin

Baseline hemoglobin will be an average of hemoglobin measurements within 28 days of Cycle 1 Day 1, excluding measurements within 7 days following RBC transfusion.

Baseline Transfusion Burden

Baseline transfusion burden will be calculated as the total amount of RBC transfusion during the 8 weeks prior to Cycle 1 day 1.

Baseline for Other Parameters

Baseline erythropoietin (EPO) is defined as the maximum test value within 28 days of Cycle 1 Day 1. For all other parameters, baseline is defined as the last observation on or prior to Cycle 1 Day 1.

End of Treatment (EOT)

Procedures and evaluations for the end of treatment visit should be performed on Day 113 (± 7 days) (28 days after the last dose of ACE-536).

Post Treatment Follow-Up (PTFU)

Procedures and evaluations for the post treatment follow-up visit should be performed on Day 141 (± 7 days) (28 days after EOT visit).

End of Study (EOS)

Procedures and evaluations for the end of study visit should be performed on Day 169 (± 7 days) (56 days after the Day 113/EOT visit).

Patients who discontinue treatment early should complete the end of treatment visit at the time of discontinuation and complete the post-treatment follow-up (PTFU) and EOS follow-up visits 28 days (± 7 days) and 56 days (± 7 days) after the EOT visit.

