5.8.3. Laboratory Evaluations

Results from the following laboratory parameters, recorded at their respective time points will be summarized by dose cohort and time point:

Hematology: (Screening, Days 1, 8 and 15 of each cycle, End of Treatment, Post Treatment Follow Up and End of Study).

RBC, WBC with differential, hemoglobin, hematocrit, haptoglobin (optional), reticulocyte count, platelet count, MCV, MCH, MCHC, RDW, and nRBCs

Chemistry: (Screening, Days 1 and 15 of Cycle 1, and Days 1 and 8 of each subsequent cycle, End of Treatment and End of Study).

Sodium, potassium, chloride, carbon dioxide/bicarbonate (optional), AST, ALT, lactate dehydrogenase (LDH), total bilirubin, indirect bilirubin, alkaline phosphatase, blood urea nitrogen (BUN)/urea, creatinine, GGT, calcium, phosphorus, glucose, amylase, lipase, total protein, albumin, and uric acid

Urine: (Day 1 of Cycles 1, 2 and 4, End of Treatment and End of Study).

PH, specific gravity, protein, glucose, ketones, blood, leukocyte esterase, and nitrite, with microscopic examination if indicated; Microalbumin and creatinine

Urine Chemistry: (Day 1 of Cycles 1, 2 and 4, End of Treatment and End of Study).

Microalbumin and creatinine will be performed by the central lab; individual and mean UACRs over time (for the ITT group) will be computed

Categorical and numeric variables will be presented separately.

Actual values and changes in hematology and biochemistry laboratory values from baseline will be summarize by dose cohort and by time point.

Shift tables for the hematology and biochemistry laboratory parameters comparing values above, within and below the normal reference range at baseline to the end of treatment visit will be presented using standard reference ranges.

Peripheral blood smears are taken at Screening, Day 1 of Cycles 1, 2, and 5 and at the end of treatment visit. These data will be listed only.

All laboratory values will be listed for all patients.

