5.8.5. ECG Results

12 lead ECG results are recorded at Screening, Cycle 2 Day 1, and at the end of treatment visit. The quantitative ECG assessments (Ventricular rate, QRS width, PR interval, QTcF, interval) will be summarized at each time point by dose cohort.

ECG overall interpretation (normal, abnormal not clinically significant and abnormal clinically significant) will be presented for actual values and changes from baseline (Screening observation) to each post baseline visit [expressed as Improvement, No Change, and Deterioration] by dose cohort.

Note:

- Improvement = Abnormal Clinically Significant (CS) to Abnormal Not Clinically Significant (NCS)/Normal, Abnormal NCS to Normal
- Deterioration = Normal to Abnormal NCS/CS, Abnormal NCS to Abnormal CS
- No change = Normal to Normal, Abnormal NCS to Abnormal NCS, Abnormal CS to Abnormal CS

If either result is missing for any patient, then an 'Unknown' category will be presented.

ECG results will be listed for all patients.

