¹² **End of Treatment (EOT):** Should be performed 28 days (\pm 7 days) after the last dose of ACE-536. Patients who discontinue treatment early should complete the end of treatment visit at the time of discontinuation and complete the post-treatment follow-up (PTFU) and EOS follow-up visits 28 days (\pm 7 days) and 56 days (\pm 7 days) after the EOT visit.

¹³ **End of Study (EOS):** Should be performed 56 days (\pm 7 days) after the Day 113/EOT visit.

¹⁴ **Day 85 \pm 2 days** is the last possible study day that ACE-536 may be administered, regardless of the cycle.

¹⁵ If a **dose delay** is required per the dose modification rules the patient will not be dosed. The patient will return weekly to assess hematology results and adverse events until the patient is eligible to administer the next dose of ACE-536. The patient should resume the study at the planned dosing cycle (e.g. if the patient missed a dose at C4D1, then they would resume dosing at C4D1 and not skip to C5D1). Note: study days may vary if a dose delay occurred during the treatment period.

¹⁶ If the patient has a **positive ADA** result at their last assessment, the patient may be asked to return approximately every three months for additional testing, until a negative result is obtained or the result is considered stabilized.

¹⁷ For the **first dose of ACE-536**, dosing should occur after a minimum of 7 days post-transfusion and a minimum of 24 hours prior to a scheduled transfusion.

¹⁸ **Expansion cohorts** only, administration of quality of life questionnaires. Quality of life questionnaire not required for expansion cohort 2 or 3 patients at C5D1.

¹⁹ **Quality of life questionnaires** should be completed at the EOT visit for patients that discontinue treatment early and for all expansion cohort 2 and 3 patients.

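### SAP 5.14.4 files safety data by fixed windows from Day 1 while the end-of-treatment visit is timed from the last dose or discontinuation, so, read literally, some dose holds and early stops take its values out of the end-of-treatment row

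*SAP*

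**What the plan says.** SAP 5.14.4 tabulates one study-day window per visit, all counted from Cycle 1 Day 1, and states: "The analysis window will be used for all safety assessments". EOT is Day 113 ± 7, post-treatment follow-up (PTFU) Day 141 ± 7 and end of study (EOS) Day 169 ± 7. Cycle visits after Day 1 have ± 3 days. The section adds that "if more than one observation exists within the analysis window, an average value will be included in the analysis".

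Other parts of the SAP time the same visits differently. SAP 5.1 and footnote 12 of the Schedule of Events (SAP Appendix 2) place EOT 28 days after the last dose, with ± 7 days. For early stops, "Patients who discontinue treatment early should complete the end of treatment visit at the time of discontinuation", with PTFU and EOS 28 and 56 days later (± 7). Footnote 14 says that Day 85 ± 2 "is the last possible study day that ACE-536 may be administered, regardless of the cycle". Footnote 15 has a held patient return weekly and then resume at the delayed cycle, and adds: "Note: study days may vary if a dose delay occurred during the treatment period".

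Three outputs use the EOT row. The hematology and biochemistry shift tables compare values against the "normal reference range at baseline to the end of treatment visit will be presented using standard reference ranges" (SAP 5.8.3). Chemistry times after Cycle 1 are given as "and Days 1 and 8 of each subsequent cycle, End of Treatment and End of Study", so there is no PTFU chemistry. For ECG, "12 lead ECG results are recorded at Screening, Cycle 2 Day 1, and at the end of treatment visit" (SAP 5.8.5).

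**The concern.** The two timing rules agree for a patient dosed on schedule and can part after a hold or an early stop. Because dosing is capped near Day 85, a 7-day hold costs the patient the last dose and moves EOT earlier, not later, while the EOT window stays where it was. The EOT value is then filed under a Cycle 5 label or under no label. The EOT row is left empty or, for some laboratory values, filled by a later follow-up visit.

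EOT is the only post-baseline point in the shift tables and one of two for ECG. The patients concerned are unlikely to be a random subset. SAP 3.2 lists adverse events, disease progression, persistent white-cell increase and peripheral blasts among the reasons to stop, and Table 4 of the supplied protocol holds doses for high hemoglobin, related Grade 3 or higher non-hematologic events and raised white-cell count.

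**Working it through.** **Inputs.** Windows from SAP 5.14.4: C5D1 Days 82–88, C5D8 89–95, C5D15 96–102, EOT 106–120, PTFU 134–148, EOS 162–176. Between and after these, Days 103–105, 121–133 and 149–161 belong to no row. Dosing interval 21 days; last permitted dosing day 85 + 2 = 87 (footnote 14); hold steps of 7 days (weekly return, footnote 15).

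**The plan's own figures.** Doses on Days 1, 22, 43, 64 and 85. EOT = 85 + 28 = Day 113; PTFU = 113 + 28 = Day 141; EOS = 113 + 56 = Day 169. All three reproduce the SAP.

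**Holds.** EOT = last dose + 28; permitted range = EOT ± 7, which is 15 days.

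| Hold | Last dose | EOT (range) | Row at nominal EOT | Permitted days that reach the EOT row |
|---|---|---|---|---|
| 7 days at C2D1, C3D1 or C4D1 | 71 (dose 5 would be Day 92, barred) | 99 (92–106) | C5D15 | 1 of 15 |
| 7, 14 or 21 days at C5D1, dose 5 forfeited | 64 | 92 (85–99) | C5D8 | 0 of 15 |
| 14 days at C2D1–C4D1 | 78 | 106 (99–113) | EOT, first day | 8 of 15 |
| 21 days at C2D1–C4D1 | 85 | 113 (106–120) | EOT | 15 of 15 |

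- First line: the 15 days split into 4 in C5D8, 7 in C5D15, 3 in no row and 1 in EOT. PTFU (99 + 28 = 127) and EOS (99 + 56 = 155) fall in no row.
- Second line: the split is 4 in C5D1, 7 in C5D8 and 4 in C5D15. PTFU (92 + 28 = 120) is filed as EOT and EOS (92 + 56 = 148) as PTFU.
- After a 7-day hold at C2D1, C3D1 or C4D1, each later cycle visit is also filed one label late: 3 visits × 3, 2 or 1 remaining dosed cycles = 9, 6 or 3 visits. Nominal 14- and 21-day holds keep EOT in its row but shift cycle labels too.
- A 28-day hold at C2D1 or C3D1 again gives last dose Day 71 and EOT Day 99.
- If each interval may vary by ± 2 days, a 7-day hold moves nominal EOT (last dose + 28) out of its row in 590 of 625 combinations at each hold position. In the other 35, shortened cycles save the fifth dose.

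**Early stops.** Let d be the EOT day, from 22 to 84 (63 calendar days, ending the day before the planned fifth dose). Since d < 106, the EOT value never reaches the EOT row.

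At exact spacing:
- EOS = d + 56 lies in 106–120 for d = 50–64: 15 days.
- PTFU = d + 28 lies in 106–120 for d = 78–84: 7 days.
- Hematology (EOT, PTFU and EOS visits): row empty on 63 − 15 − 7 = 41 days.
- Chemistry (EOT and EOS visits): row empty on 63 − 15 = 48 days.
- ECG (EOT visit only): cell empty on all 63 days.

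With the permitted ± 7 days:
- EOS spans d + 49 to d + 63 and can reach 106–120 for d = 43–71 (29 days).
- PTFU spans d + 21 to d + 35 and can do so for d = 71–84.
- Hematology is certain to be empty only for d = 22–42: 21 days.
- Chemistry is certain to be empty for d = 22–42 and 72–84: 21 + 13 = 34 days.
- ECG stays empty on all 63.

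**The case against.** The strongest reply is that the literal reading is not the only one. SAP 5.1 gives Day 113 together with last dose + 28, so Day 113 can be read as a nominal label. SAP 5.14.4 introduces its table as visit naming. Sections 5.8.3 and 5.8.5 name the end-of-treatment visit, which may mean the recorded one. Protocol section 12 ties visit windows to the previous dose, and the SAP asks to be read with the protocol. This reading is possible, but the SAP does not state it. Section 5.14.4 applies its windows to all safety assessments, its averaging rule implies assignment by date, its tolerances differ from those of the visit schedule, and the list of changes from the protocol in 5.15 does not mention visit windows. Two programmers could produce different shift tables.

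Second, a 7-day hold need not be typical. Protocol Table 4 holds at hemoglobin of 12 g/dL or more until it is below 11, and the half-life in healthy volunteers was 15.5 to 18.5 days (protocol 7.3), so longer holds are plausible. That stands: a reader might infer that every hold loses the EOT value, and the 14- and 21-day cases at C2D1–C4D1 show otherwise.

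Third, an early-stop EOT visit may coincide with an on-treatment visit while drug is still present, and filing by study day is a defensible calendar-time choice. That stands against any general claim that off-drug values contaminate treatment rows. It does not explain an empty EOT row.

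Finally, the consequence is limited. All summaries are descriptive (SAP 5.2), and all laboratory and ECG results are listed. Vital signs have no EOT time point in SAP 5.8.4, so only their cycle labels move.

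**Conclusion.** The SAP contains two timing rules for EOT and does not say which prevails. Followed literally, 5.14.4 misfiles the EOT value after a 7-day hold at C2D1–C4D1 (1 of 15 permitted days reaches the row), after a hold that forfeits dose 5 at C5D1 (0 of 15), and after any early stop with EOT on Days 22–84. The conflict is internal to the SAP and does not depend on which protocol version is used.

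The hold results rest on nominal 21-day intervals and one hold per patient. The early-stop splits of 41 and 48 empty days hold only at exact + 28 and + 56 spacing; with the permitted tolerance, 21 hematology days and 34 chemistry days are certain to be empty. These are counts of calendar days. A reader might take them as patient rates, but the documents give no hold or early-stop rate, so the share of patients affected is unknown.

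A reader might also infer that safety data are lost or that the main results are biased. The documents do not support that: treatment-emergent adverse events, dose-limiting toxicities, listings and the primary endpoint do not depend on these windows. The effect is confined to the descriptive hematology and chemistry shift tables, the ECG summary and the cycle labels of by-visit tables. It should be corrected because the remedy is cheap.

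**What to change.** Change SAP 5.14.4 only:

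- Cycle Day 1 = the actual dosing day; Day 8 and Day 15 = that dose + 7 and + 14 days (± 3).
- EOT = the recorded EOT or discontinuation visit, expected at last dose + 28 days (± 7) for patients who do not stop early.
- PTFU and EOS = the recorded visits, expected at EOT + 28 and + 56 days (± 7).
- Visits at which a dose was held, including a held C5D1, are unscheduled.
- The recorded EOT visit takes precedence over any overlapping Day 8, Day 15 or unscheduled label, is not averaged with other visits, and supplies the value for the 5.8.3 shift tables and the 5.8.5 ECG summary.

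The precedence rule is needed. A held C5D1 visit on Day 85 is last dose + 21 (85 − 64), already inside a window of last dose + 21 to + 35, and a discontinuation visit can fall on a Day 8 or Day 15 date.

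The cost is one SAP table and its derivation program, before database lock. No new data and no protocol change are needed. The downside is that, for delayed patients, rows line up by cycle rather than by days since Day 1.

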5.15. Changes in Conduct or Planned Analyses from the Protocol

Major changes between SAP and the planned analysis in Protocol Amendment 6 are described below:

Item	Difference between Protocol and SAP
NTD/TD	In SAP, the terms LTB/HTB are used in place of NTD/TD in protocol.
Secondary objectives: time to and duration of mHI-E	The secondary endpoints time to and duration of mHI-E will not be analyzed.
Efficacy Evaluable Population (EE)	Analysis on Efficacy Evaluable population will not be performed. All analyses are on ITT population
Definition of baseline hemoglobin	Protocol definition: Baseline hemoglobin will be the average of at least two measures (not influenced by transfusion within 7 days of measurement); one measure performed within one day prior to Cycle 1 Day 1 and the other performed 7-28 days prior to Cycle 1 Day 1. This definition is revised in this SAP to reflect the derivation rule implemented for this study.

7. APPENDICES

7.1. Appendix 1 - List of Abbreviations

Abbreviation	Definition
ActRIIB	Activin receptor IIB
AE	Adverse Event
ALT	Alanine aminotransferase
AML	Acute myeloid leukemia
AST	Aspartate aminotransferase
AUC	Area under the concentration-time curve
BSAP	Bone specific alkaline phosphatase
BUN	Blood urea nitrogen
CI	Confidence interval
C _{max}	Maximum concentration
CRF	Case report form
CRO	Contract research organization
CTX	C-telopeptide of type I collagen
DLT	Dose-limiting toxicity
ECG	Electrocardiogram
EE	Efficacy Evaluable
EOS	End of Study
EPO	Erythropoietin
EOT	End of Treatment
FACT-An	Functional Assessment of Cancer Therapy-Anemia Scale
GDF	Growth and differentiation factor
Hgb	Hemoglobin
HTB	High Transfusion Burden
ITT	Intent-to-Treat
IPSS	International Prognostic Scoring System
LDH	Lactate dehydrogenase
LTB	Low Transfusion Burden
mHI-E	Modified erythroid response
MedDRA	Medical Dictionary for Regulatory Activities
MCH	Mean corpuscular hemoglobin
MCHC	Mean corpuscular hemoglobin concentration

Abbreviation	Definition
MCV	Mean corpuscular volume
NCI-CTCAE	National Cancer Institute-Common terminology criteria for adverse events
nRBCs	Nucleated red blood cells
NTBI	Non-transferrin bound iron
PD	Pharmacodynamic
PK	Pharmacokinetic
QoL	Quality of life
RBC	Red blood cell
RDW	Red blood cell distribution width
RS	Ringsideroblasts
SAE	Serious adverse event
SAP	Statistical analysis plan
SD	Standard deviation
SRT	Safety review team
T _{1/2}	Elimination half-life
TIBC	Total iron binding capacity
T _{max}	Time to maximum concentration
WBC	White blood cell
WHO	World Health Organization

7.2. Appendix 2 - Schedule of Events

	Screen	Treatment Period																	Follow up period			
		Cycle 1				Cycle 2			Cycle 3			Cycle 4			Cycle 5			EOT ¹²	Post-Treatment Follow Up	EOS ¹³		
		C1D1 ²	C1D8	C1D11	C1D15	C2D1 ^{2,15}	C2D8	C2D15	C3D1 ^{2,15}	C3D8	C3D15	C4D1 ^{2,15}	C4D8	C4D15	C5D1 ^{2,15}	C5D8	C5D15					
	Day -28	Day 1	Day 8 (± 1d)	Day 11 (± 1d)	Day 15 (± 1d)	Day 22 (± 2d)	Day 29 (± 2d)	Day 36 (± 2d)	Day 43 (± 2d)	Day 50 (± 2d)	Day 57 (± 2d)	Day 64 (± 2d)	Day 71 (± 2d)	Day 78 (± 2d)	Day 85 (± 2d)	Day 92 (± 2d)	Day 99 (± 2d)	Day 113 (± 7d)	Day 141 (± 7d)	Day 169 (± 7d)		
Informed consent	X																					
Inclusion/Exclusion	X	X																				
Medical history	X																					
QoLQuestionnaires ¹⁸	X																	X ¹⁸		X ¹⁹	X	
Physical examination	X	X				X			X			X			X				X		X	
Vital signs ¹	X	X	X		X	X	X	X	X	X	X	X	X	X	X	X	X	X				
ECOG Status	X								X			X							X		X	
ECG (12 lead)	X					X														X		
Bone marrow aspirate/biopsy ³	X								X ³										X			
Serum iron studies ⁴	X	X				X	X		X			X			X				X	X	X	
Serum folate and B ₁₂	X																					
Erythropoietin levels	X	X	X		X	X						X							X	X	X	
Hematology ⁵	X	X	X		X	X	X	X	X	X	X	X	X	X	X	X	X	X	X	X	X	
Peripheral blood smear	X	X				X												X		X		
Serum chemistry ⁶	X	X			X	X	X		X	X		X	X		X	X		X			X	
Urinalysis and Urine Chemistry ⁷		X				X						X							X		X	
Anti-drug antibody ¹⁶		X										X							X		X ¹⁶	
PK collection		X	X	X	X	X	X					X			X	X	X	X	X	X	X	
PD biomarkers ⁸		X				X			X			X			X				X		X	
Bone biomarkers ⁹		X										X							X			
Pregnancy test ¹⁰	X	X				X			X			X			X			X		X		X
Evaluate transfusion frequency ¹¹	X	X				X			X			X ²			X			X	X	X	X	

Concomitant medications and AEs	X	X	X	X	X	X	X	X	X	X	X	X	X	X	X	X	X	X	X
Administer ACE-536 ¹⁷		X				X ¹⁴													

¹ **Vital signs:** Weight, heart rate, systolic and diastolic blood pressure, respiration rate and temperature (measured in degrees Celsius). Height is measured only at Screening.

² **Study procedures** must be done prior to administration of study drug.

³ **Bone marrow aspirate/biopsy** including cytogenetics at screening must be performed \leq 3 months prior to C1D1 for evaluation of patient eligibility and other PD biomarkers to be determined (e.g., GDF15, GDF8, and GDF11).

- For all patients, at the end of treatment visit, a bone marrow aspirate must be performed (a bone marrow biopsy is optional).
- Dose escalation cohorts and expansion cohort 1 patients only: a bone marrow aspirate must be performed within 21 days after C3D1 (a bone marrow biopsy is not required). Note: A bone marrow aspirate is not required within 21 days after C3D1 for expansion cohort 2 or 3 patients.
- Dose escalation cohorts and expansion cohort 1 patients only: If hemoglobin increases \geq 2 g/dL, an optional bone marrow aspirate can be performed within 7 days of the result.

⁴ **Iron Studies:** Serum iron, TIBC, transferrin, soluble transferrin receptor, NTBI, ferritin.

⁵ **Hematology:** RBC, WBC with differential, hemoglobin, hematocrit, nRBC, reticulocyte count, platelet count, peripheral blasts (on dosing days only: C1D1, C2D1, C3D1, C4D1, C5D1), MCV, MCH, MCHC, and RDW. On dosing days, hemoglobin values are to be drawn and resulted (up to 1 day) prior to dosing (see Section **Error! Reference source not found.**, Patient Dose Modification Rules). Historical hemoglobin data will be collected for 24 weeks, where available, prior to C1D1. During the screening period, hemoglobin will be measured twice; one measure performed within one day prior to Cycle 1 Day 1 and the other performed 7-28 days prior to Cycle 1 Day 1. Neither hemoglobin measure should be influenced by transfusion within 7 days of measurement.

⁶ **Chemistry:** Sodium, potassium, AST, ALT, lactate dehydrogenase (LDH), total bilirubin, direct bilirubin, alkaline phosphatase, blood urea nitrogen (BUN)/urea, creatinine, GGT, calcium, phosphorus, glucose, amylase, lipase, total protein, albumin, and uric acid.

⁷ **Urinalysis by dipstick analysis (local lab):** pH, specific gravity, protein, glucose, ketones, blood, leukocyte esterase, and nitrite, with microscopic examination if indicated. **Urine Chemistry (central lab):** Microalbumin and creatinine.

⁸ **PD Biomarkers:** Hepcidin, GDF15, GDF8, GDF11, and others to be determined.

⁹ **Bone Biomarkers:** BSAP and CTX. Not required for expansion cohort 2 or 3 patients.

¹⁰ **Pregnancy test:** (urine or serum) is required for female patients of child bearing potential at screening and prior to each dose of ACE-536.

¹¹ **Transfusion history** will be collected for 24 weeks, where available, prior to C1D1.

¹² **End of Treatment (EOT):** Should be performed 28 days (\pm 7 days) after the last dose of ACE-536. Patients who discontinue treatment early should complete the end of treatment visit at the time of discontinuation and complete the post-treatment follow-up (PTFU) and EOS follow-up visits 28 days (\pm 7 days) and 56 days (\pm 7 days) after the EOT visit.

¹³ **End of Study (EOS):** Should be performed 56 days (\pm 7 days) after the Day 113/EOT visit.

¹⁴ **Day 85 \pm 2 days** is the last possible study day that ACE-536 may be administered, regardless of the cycle.

¹⁵ If a **dose delay** is required per the dose modification rules the patient will not be dosed. The patient will return weekly to assess hematology results and adverse events until the patient is eligible to administer the next dose of ACE-536. The patient should resume the study at the planned dosing cycle (e.g. if the patient missed a dose at C4D1, then they would resume dosing at C4D1 and not skip to C5D1). Note: study days may vary if a dose delay occurred during the treatment period.

¹⁶ If the patient has a **positive ADA** result at their last assessment, the patient may be asked to return approximately every three months for additional testing, until a negative result is obtained or the result is considered stabilized.

¹⁷ For the **first dose of ACE-536**, dosing should occur after a minimum of 7 days post-transfusion and a minimum of 24 hours prior to a scheduled transfusion.

¹⁸ **Expansion cohorts** only, administration of quality of life questionnaires. Quality of life questionnaire not required for expansion cohort 2 or 3 patients at C5D1.

¹⁹ **Quality of life questionnaires** should be completed at the EOT visit for patients that discontinue treatment early and for all expansion cohort 2 and 3 patients.

